### *Primary endpoint*

- Mechanical ventilation within four days of birth

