#### *Management of RDS*

The European Consensus Guidelines for the management of RDS recommend stabilisation of the infant using non-invasive respiratory support such as high flow and continuous positive airway pressure (CPAP). The infant's oxygen requirements are monitored and should the fraction of inspired oxygen (FiO2) required increase above 30% in infants under 26 weeks gestational age or 40% in infants over 26 weeks gestational age, then surfactant administration is recommended. Surfactant is normally administered by endotracheal tube whilst the infant is sedated, but the European Consensus Guidelines recommend the Intubate-SURfactant-Extubate (INSURE) method (where the endotracheal tube is extubated within 1 hour) or by less/minimally invasive surfactant administration using a thin catheter to deliver surfactant whilst the infant is spontaneously breathing.

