### *Primary objective*

- To determine whether the first dose of surfactant (100-130 mg/kg compared to 170-200 mg/kg) has an effect on the requirement for mechanical ventilation within four days of birth

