## NNRD Fields

Surfactant can be administered prophylactically (usually within the delivery room) or as rescue (usually within the neonatal ward). If surfactant is given prophylactically, it is assumed that this is the first administration.

If administered prophylactically, it is proposed that the following data items are added under the 'NNUEpisodes-Labour & Delivery' category within the electronic record:

	Question	Answer
1	Volume of surfactant administered in millilitres (mL)	[free text box]
2	Method of surfactant administration	
 
• Endotracheal tube
 
• INSURE (endotracheal tube in place for 15 minutes or less)
 
• Thin catheter for minimally invasive/less invasive surfactant administration
 
• Other
 

3	Time of initial surfactant administration	[free text]
4	Specify any analgesics and/or sedatives used for surfactant administration (drug and dose)	[free text]

Surfactant can also be administered in a rescue setting, usually within the neonatal unit. In this setting, the frequency of administration is captured (i.e. whether this is the infant's first, second or third dose). The following fields are proposed under the 'Respiratory-Daily' category:

	Question	Answer
1	Volume of surfactant administered in first dose, millilitres (mL)	[free text box]
2	Specify the method of surfactant administration	
 
• Endotracheal tube
 
• INSURE (endotracheal tube in place for 15 minutes or less)
 
• Thin catheter for minimally invasive/less invasive surfactant administration
 
• Other
 

3	How many doses of surfactant were administered today?	[Free text box]
4	Time of initial surfactant administration	[free text]
5	Specify any analgesics and/or sedatives used for surfactant administration (drug and dose)	[free text]
6	FiO 2 at point of decision to administer surfactant	
 
• < 30 %
 
• 30- 39 %
 
• 40 - 49 %
 
• 50 - 59 %
 
• ≥ 60 %
 

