## b. Inclusion/Exclusion Criteria

### Inclusion Criteria:

- Gestational age of  $36^{+6}$  weeks or less
- Treated with surfactant
- Record of birth-weight available
- Infants born after the initiation date of the study
- Parental opt-out consent

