### Exclusion Criteria:

- Gestational age of  $37^{+0}$  weeks and above

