## 6. Data Analysis

The primary objective of the study is to compare the two dosing groups (100-130 mg/kg and 170-200 mg/kg) in terms of the proportions of infants who require mechanical ventilation within four days of birth. This comparison will be undertaken primarily through propensity score matching with the key sensitivity analysis comparing the unmatched dosing groups.

The propensity score model will be a logistic regression model with binary 'outcome' corresponding to dosing group and with the following baseline factors included in the model; birth weight, gestational age, sex, antenatal steroids, inborn, age at first dose, and baseline FiO2. This analysis will be based on the modified Intention-to-Treat population (mITT) defined as all patients who satisfy the inclusion/exclusion criteria, who provide complete data on each of the baseline factors considered for inclusion in the propensity model and who are evaluable for the primary endpoint.

Following 1 to 1 matching between the dosing groups 100-130 mg/kg and 170-200 mg/kg using a caliper of 0.025, an analysis of the matched cohorts will be based on a logistic regression model with the primary endpoint, requiring mechanical ventilation within 4 days of birth, as the response and dosing group plus each of the covariates listed used in the propensity score model included as terms in this analysis model. The key sensitivity analysis will compare the dosing groups in the full mITT population using the same modelling structure.

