**The effect of surfactant dose on outcomes in preterm infants with RDS**

NNUEpisodes	Discharge details	Cause of death	Cause of death	DEATH CAUSE ICD CODE (DURING NEONATAL CRITICAL CARE PERIOD)	an 6	ICD-10	Specify the major reasons for death of the baby from the list of International Classification of Diseases (ICD) as corresponding with death certificate.	Used to compare outcomes for babies
NNUEpisodes	Discharge details	Discharge:: Oxygen	Discharge Oxygen	RECEIVING OXYGEN THERAPY ON DISCHARGE INDICATOR	N	Delivered from Daily Data Item N No Y Yes	Item specifies if the baby is receiving and is dependant on oxygen therapy on discharge home.	Used to compare outcomes for babies.
NNUEpisodes	Discharge details	Clinical diagnoses at discharge	DiagnosesAtDischarge	DIAGNOSIS (ICD RECORDED ON DISCHARGE FROM NEONATAL CRITICAL CARE) and/or DIAGNOSIS (SNOMED CT ON DISCHARGE FROM NEONATAL CRITICAL CARE)	an 16/n18	ICD-10 and/or SNOMED CT Can be derived from daily records	Specify all the applicable diagnoses for this baby if not already recorded in the daily diagnoses	Used to monitor infant care, evaluate health status and outcomes
Daily	Respiratory	Respiration: Respiratory support device	Respiratory support	RESPIRATORY SUPPORT MODE (NATIONAL NEONATAL DATA SET)	N1	1 Endotracheal tube2 Tracheostomy3 Nasal cannula4 Nasopharyngeal cannula5 Face mask	Type of respiratory support device any time during the 24 hour period (00.00-23.59)	Used to determine level of care
Daily	Respiratory	Respiration: Surfactant given today	DaySurfactantGiven	SURFACTANT GIVEN INDICATOR (ON NEONATAL CRITICAL CARE DAILY CARE DATE)	an 1	N No Y Yes	Records if baby received any dose of surfactant in this day while in the neonatal unit. Surfactant given at delivery/resuscitation is a data	Used to determine health status of infant

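### The primary endpoint does not require ventilation to start after the first surfactant dose, and ventilation status at dosing is neither excluded, matched nor adjusted for

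*Protocol*

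**What the plan says.** The primary objective asks whether the first dose, 100-130 against 170-200 mg/kg, "has an effect on the requirement for mechanical ventilation within four days of birth". The endpoint list ("Mechanical ventilation within four days of birth") and section 6 keep the same window, counted from birth.

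The only treatment criterion in section 4b is "Treated with surfactant". The only exclusion is a gestation of 37+0 "weeks and above". No upper limit is set on age at first dose. The NNRD Fields section includes both settings: "Surfactant can be administered prophylactically (usually within the delivery room) or as rescue". The background states: "Surfactant is normally administered by endotracheal tube whilst the infant is sedated".

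Section 6 limits the mITT population to eligible infants with complete baseline factors "who are evaluable for the primary endpoint", and does not define evaluability. The propensity model, and the outcome model that reuses its covariates, contain birth weight, gestational age, sex, antenatal steroids, inborn status, age at first dose and baseline FiO2. Ventilation status at dosing, route of administration and prophylactic or rescue setting are absent.

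Appendix A records the support device once per day: "Type of respiratory support device any time during the 24 hour period (00.00-23.59". Support mode is a separate daily field.

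**The concern.** A dose cannot cause ventilation that preceded it. As written, an infant already ventilated at first dosing is an event by definition. So is any infant first dosed after day four who had been ventilated earlier, since its whole endpoint window closed before exposure.

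Two consequences follow. If the two dosing groups contain different shares of such infants, the comparison shows a difference that has nothing to do with dose. Nothing in the matching or the outcome model targets that imbalance, and a larger sample does not remove it. If the shares are equal, the automatic events are noise that pulls a true difference towards zero.

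The protocol uses the at-risk idea elsewhere: the FiO2 ROC analysis in section 6 is framed around infants who fail non-invasive support. The primary comparison has no such condition. The dose ROC analysis and the exploratory comparison of administration methods use the same endpoint and share the problem.

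**Working it through.** **Inputs.** From section 4a: event rates 60% and 45%, two-sided 5%, 80% power, 25% of the smaller group unmatched, smaller-group share 45%, 40% or 35%, total 1300. The share f already ventilated at first dose is not in the protocol and is varied.

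**The plan's own figure.** With unpooled variance, n per matched group = (1.960 + 0.842)² × [0.60×0.40 + 0.45×0.55] / 0.15² = 171. The total is 2 × 171 / 0.75 / (smaller share), which gives 1014, 1140 and 1303, as in the table. The table divides both matched groups by the smaller group's share. If instead each matched infant of the smaller group yields one pair, 1300 infants at 35%/55% give 1300 × 0.35 × 0.75 = 341 pairs.

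**Unequal shares, no dose effect.** Let r be the event rate in infants not ventilated at dosing. The spurious difference is (f₁ − f₂)(1 − r). With r assumed to be 40%:
- 50% vs 30% ventilated: (0.50 + 0.50×0.40) − (0.30 + 0.70×0.40) = 0.70 − 0.58 = 12 points.
- 30% vs 20% ventilated: 0.10 × 0.60 = 6 points.

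The study is designed to detect 15 points.

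**Equal shares, reading A: 60% and 45% apply to infants not yet ventilated.** Observed rate = f + (1 − f)p, so the difference is 15(1 − f) points. Power is the two-proportion normal approximation with pooled variance under the null.

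| f | Observed rates | Difference (points) | Power, 341 pairs |
|---|---|---|---|
| 0 | 60.0% vs 45.0% | 15.0 | 98% |
| 25% | 70.0% vs 58.8% | 11.25 | 87% |
| 50% | 80.0% vs 72.5% | 7.5 | 63% |
| 75% | 90.0% vs 86.3% | 3.75 | 33% |

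With only the 171 pairs the formula requires, power is 80% at f = 0, 54% at 30% and 37% at 50%.

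**Equal shares, reading B: 60% and 45% already describe the whole groups.** Planned power is unchanged. The implied rates in infants still at risk are (0.60 − f)/(1 − f) and (0.45 − f)/(1 − f): 42.9% vs 21.4% at f = 30%, and 33.3% vs 8.3% at f = 40%. At f = 45% the second rate is zero, so f cannot be larger. The relative reduction that dose must achieve in these infants rises from 25% (1 − 45/60) to 50% at f = 30% and 75% at f = 40%.

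**Restricting to infants at risk, reading A.** At f = 25%, 50% and 75%, 341(1 − f) leaves about 255, 170 and 85 pairs at 60% vs 45%. Power is about 93%, 79% and 50% (93%, 80% and 51% with unpooled variance), against 87%, 63% and 33% when the automatic events are kept.

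**The case against.** Several stronger readings are tempting, and the protocol does not support them.

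*That the study is underpowered.* Section 4a states 60% and 45% as proportions in the dosing groups. Taken literally, that is reading B, under which planned power does not fall and values of f above 45% are impossible. The power losses belong to reading A only. The rates are also given for 72 hours, not four days, so they fit neither reading exactly.

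*That every tube placed to give surfactant is an event.* Device and mode are separate daily fields, the endpoint is ventilation and not intubation, and INSURE has its own route category. How device and mode combine is not stated, and may properly be left to the SAP. The background sentence on the usual route goes on to report guidelines recommending INSURE or a thin catheter, and an endotracheal route does not show that ventilation came before the dose.

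*That every infant ventilated in the delivery room enters the analysis.* FiO2 at the decision to treat is listed among the rescue fields and not the prophylactic ones. If that field is the baseline FiO2, the complete-data rule may drop infants dosed in the delivery room. Infants intubated at birth and dosed later, or ventilated in the unit before dosing, would remain.

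*That late first dosing is a large problem.* The rationale concerns treatment in the immediate postnatal period, and age at first dose is a covariate. The case is possible because no limit is set, but nothing suggests that it is common.

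The listed covariates may also reduce an imbalance in ventilation status, but none of them identifies which infants were ventilated. What remains untouched is that no rule orders ventilation after dose. Leaving evaluability undefined does not repair this: an infant already ventilated has a known outcome and on the ordinary reading is evaluable, as an event.

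**Conclusion.** The point holds. The endpoint, eligibility, analysis population and covariates are all fixed in the protocol, and together they count events that the dose could not have caused and leave ventilation status at dosing uncontrolled. This concerns the validity of the primary comparison.

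The size is unknown because f is not given. The bias depends on f differing between the groups after matching: 12 points is the result for 50% vs 30% with a 40% event rate in the rest, and its direction cannot be read from the protocol. Dilution to 15(1 − f) points holds only if 60% and 45% apply to infants not yet ventilated. A reader should infer neither a definite loss of planned power nor that delivery-only intubations count as events.

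**What to change.** Make the primary comparison one of mechanical ventilation that starts after the first dose and within four days of birth, in infants not recorded as ventilated before that dose and first dosed within the window. Classify pre-dose status by a prespecified rule using resuscitation method (code 15, intubation), route and time of first dose, and daily device and mode. State whether an intubation used only to deliver surfactant counts. Restate the event rates for this set and for the four-day window. Keep the all-infant endpoint as a sensitivity analysis, with ventilation status at first dose added to the matching and outcome models. Apply the same definition to the dose ROC analysis and the exploratory analysis of administration method.

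The cost is an amendment to the endpoint and analysis set, with no new data fields. The primary set becomes smaller and answers a narrower question; under reading A it still has more power than the diluted comparison, but at f = 75% only about 50%. Pre-dose status will be imperfect: support is recorded daily, dose time is free text, and an endotracheal route does not separate infants already ventilated from those intubated to receive the dose. Counting only ventilation on a later calendar day than the dose is workable, but it misses ventilation confined to the dosing day and would count an infant wrongly classed as unventilated who simply stayed on the ventilator.

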### *Secondary endpoints*

- Number of doses of surfactant
- Respiratory support at day 28 post birth
- Respiratory support at  $36^{+0}$  weeks gestational age
- Duration of respiratory support
- Requirement for  $O_2$  at discharge home
- Respiratory support at 2 years

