#### *Surfactant dose*

The licensed dose of surfactant for preterm infants with RDS is 100 to 200mg/kg. A dose of 200mg/kg reduces FiO2 requirements and the need for redosing as well as indicating possibility of reduced mortality and oxygen requirement at 36 weeks post menstrual age. A pharmacokinetic study has also demonstrated that a dose of 200mg/kg results in a higher half-life of surfactant compared to the 100mg/kg.

*Administration techniques*

The drive towards minimally invasive treatments for premature infants as well as the difficulties associated with intubation for surfactant delivery has led to innovations in surfactant administration. Minimally invasive surfactant administration (MIST) or less invasive surfactant administration (LISA) are techniques that use a thin catheter (Angiocath or nasogastric tube) to deliver surfactant whilst the infant is spontaneously breathing and this method is gaining popularity across Europe. A recent meta-analysis found that the use of LISA/MIST has reduced the composite outcome of death or bronchopulmonary dysplasia (BDP) at 36 weeks, need for mechanical ventilation within 72 hours of birth, or need for mechanical ventilation anytime during the neonatal intensive care stay.

Use of the LISA/MIST techniques of surfactant administration also supports the drive towards non-invasive methods of ventilatory support, as no intubation is required to instil the surfactant, in contrast to the intubate-surfactant-extubate (INSURE) method.

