### *Exploratory endpoints*

- Incidence of complications such as retinopathy of prematurity, and periventricular haemorrhage
- Development at 2 years
- Bayley III score at 2 years

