### 3. Research Design

It is proposed to minimise data collection requirements for this study through incorporation into routine clinical care. The data items required all form part of what would normally be recorded in a patient's case records. Hence it is proposed to obtain these from the Neonatal Network Research Database (NNRD).

The Neonatal Network Research Database (NNRD) is an electronic platform where neonatal patient data on all admissions to a National Health Service (NHS) neonatal unit in England, Scotland or Wales are recorded. Clinical data on all admissions to NHS neonatal units are entered by healthcare professionals, as part of routine clinical practice, onto electronic patient record systems at the point of care; from these data, approximately 450 data items (the Neonatal Data Set, an NHS Information Standard) are extracted quarterly to form the NNRD. Data held in the NNRD are used for audits, research, service evaluations and quality improvement projects.

A small number of additional data items not currently held in the NNRD, are required for this study. They are however all items that would normally be recorded in the patient's case notes; hence it is proposed to incorporate these into the electronic data capture system. Specific Research Ethics Approval will be sought for this study.

Multiple centres across the UK will be selected to participate. The parents of eligible babies will be approached for op-out consent for their child's data to be included in the study.

The study will continue recruiting until 1300 babies have been consented, and will remain open until 2 year follow up data has been obtained for those babies born < 30 weeks gestation. There will be no further follow up in those babies that have no data available at the 2 year follow-up.

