### a. Comparative fields

In order to investigate whether surfactant dose affects neonatal outcomes, the following data will be obtained from the NNRDs:

	NNRD field	Purpose of using this field for this study
1	Demographics > Birth weight	Using this field alongside the volume of surfactant used, the dose of surfactant will be calculated.
2	Demographics > Sex of the baby (phenotypic)	Characterisation of cohort
3	Demographics > Gestation weeks and day	Inclusion/exclusion criteria
4	Antenatal > Were steroids given during pregnancy?	Characterisation of cohort
5	Antenatal > Number of antenatal steroid courses given	Characterisation of cohort
6	Labour & delivery > Methods of resuscitation	Characterisation of cohort
7	Labour & delivery > Drugs used during resuscitation	Characterisation of cohort
8	Labour & delivery > Was surfactant given during resuscitation?	Characterisation of cohort
9	Respiratory > Respiration: Surfactant given today	Inclusion/exclusion criteria
10	Discharge details > Discharge time and date (anonymised)	Duration of hospitalisation, age at discharge
11	Discharge details > Date of death and time - anonymised	Calculation of mortality
12	Discharge details > cause of death	Determination of outcomes
13	Discharge details > Discharge oxygen	To investigate whether the dose of surfactants can affect whether infants are discharged on oxygen.
14	Respiratory > Respiratory support device and support mode (daily)	To investigate whether using there is a correlation between surfactant dose and respiratory device
16	Discharge details > Clinical diagnoses at discharge	To correlate the dose of surfactant, and/or method of surfactant administration is related to clinical diagnoses at discharge
17	Retinopathy of prematurity > ROP stage*	To determine whether the dose of surfactant is related to the severity of retinopathy of prematurity
18	Cranial ultrasound scan > IVH**	To determine whether the dose of surfactant is related to the severity of periventricular haemorrhage

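### The respiratory-support endpoints make no provision for death and no mortality endpoint is listed, so a mortality difference between dose groups can distort or drop out of the comparison; separately, the 2-year follow-up scope is inconsistent

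*Protocol*

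**What the plan says.** The secondary endpoint list in section 2b of the protocol has, among others, "Respiratory support at day 28 post birth", the same status at 36 weeks, "Duration of respiratory support", oxygen at discharge home and "Respiratory support at 2 years". Each is a bare status or duration. The secondary objectives limit the day-28 and 36-week outcomes to infants born at 32 weeks or less; the endpoint list omits that limit. Neither place says how an infant who has died is counted, and mortality is not a primary, secondary or exploratory endpoint.

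Death does appear elsewhere. The table in section 3a extracts date of death for "Calculation of mortality", and cause of death as well. The background in section 2a describes 200 mg/kg as "indicating possibility of reduced mortality". It also cites a meta-analysis in which a technique of administration "reduced the composite outcome of death or bronchopulmonary dysplasia". Section 6 gives one general sentence on secondary and exploratory analyses and says nothing about deaths.

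On the 2-year outcomes, neither "Respiratory support at 2 years" nor "Bayley III score at 2 years" has a gestation limit, and infants up to 36+6 weeks are eligible. Section 3 keeps the study open until "2 year follow up data has been obtained for those babies born" before 30 weeks, and does not pursue missing 2-year records. Sections 5 and 9b time the final analysis and the end of the research by the last or final infant's 2-year point, with no gestation limit.

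**The concern.** An infant who dies on day 5 is not on support at day 28 or 36 weeks, contributes at most five days of support, and does not go home on oxygen. On the literal wording, each of these is the favourable result. If the two doses differ in mortality, which the protocol itself raises as a possibility, the dose with fewer deaths keeps more infants alive who can then be counted as on support. The mortality difference itself is not among the stated comparisons. Propensity matching does not help, because it balances baseline factors and death occurs after dosing.

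The 2-year outcomes raise a different problem. The population they are defined for is wider than the one that section 3 waits for, and the protocol's sections disagree on which applies.

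**Working it through.** The protocol gives no figure for these endpoints, so there is none to reproduce. The check is on what the definitions imply.

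Inputs, all assumed because the protocol gives no mortality or support rates by dose:
- m_L, m_H: mortality before the assessment in the lower- and higher-dose groups; d = m_L − m_H.
- s: proportion on support among infants who would survive on either dose, taken as equal in both groups (no dose effect on support itself).
- q: proportion on support among the additional survivors on the higher dose.

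Difference in rates, higher minus lower dose (positive means the higher dose looks worse):
- Death counted as off support: [s(1 − m_L) + qd] − s(1 − m_L) = qd. This is positive whenever q > 0.
- Survivors only: [s(1 − m_L) + qd]/(1 − m_H) − s = d(q − s)/(1 − m_H). This is positive only if q > s, zero if q = s, and negative if q < s.
- Death or support: [m_H + s(1 − m_L) + qd] − [m_L + s(1 − m_L)] = −d(1 − q). This is never positive when d > 0.

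Illustration with m_L = 10%, m_H = 7%, s = 40%:

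| Handling of death | Lower dose | Higher dose, q = 40% | Higher dose, q = 100% |
|---|---|---|---|
| Death as off support | 0.90 × 0.40 = 36.0% | 0.93 × 0.40 = 37.2% | 0.36 + 0.03 = 39.0% |
| Survivors only | 40.0% | 40.0% | 0.39/0.93 = 41.9% |
| Death or support | 36.0 + 10 = 46.0% | 37.2 + 7 = 44.2% | 39.0 + 7 = 46.0% |

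Wider assumed range (m_L 5–15%, d 1–5 points, s 30–50%, q 75–100%): the higher dose looks 0.8 to 5.0 points worse with death as off support and 0.3 to 3.9 points worse among survivors. The composite difference runs from 0 to −1.3 points.

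The 2-year outcomes need no arithmetic. Set side by side, the objectives and endpoints cover every eligible infant up to 36+6 weeks, section 3 waits only for those born before 30 weeks, and sections 5 and 9b wait for the last or final infant whatever the gestation. These cannot all define one analysis population. In addition, Appendix A labels the date-of-death field as covering the neonatal critical care period, so deaths between discharge and 2 years may not be in it.

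**The case against.** The best case against the point is that the protocol states no rule for deaths at all. It does not say that a death is a success, nor that it is dropped. Section 10 refers to an agreed analysis plan that is not shown, and how deaths enter an analysis is often settled there. Date and cause of death are extracted, so mortality can be reported. Oxygen at discharge home and the 2-year scores can only be measured in survivors anyway. The rates above are assumed. Under the splits in section 4a with 25% unmatched, 1300 infants give about 1300 × 0.35 × 0.75 = 341 to 1300 × 0.45 × 0.75 = 439 matched pairs. At a 40% rate the standard error of a difference is then √(0.48/439) = 3.3 to √(0.48/341) = 3.8 points, before the limit to 32 weeks. The 1.2- to 3.0-point artefacts of the death-as-off-support rows in the table are smaller than that.

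Much of this stands. The size is assumed and modest, and the composite has a cost of its own: with q = 100% it shows 46% vs 46% and hides a 3-point mortality difference. It does not remove the point. Which outcomes the study has, and whether mortality is one of them, is fixed in the protocol, which already sets an endpoint population through the 32-week limit. A bias of this kind also does not shrink with more infants.

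Four stronger readings are tempting and are not supported:
- A reader might infer that any survivors-only analysis is biased against the dose with fewer deaths. The formula shows no bias at q = s and a reversed bias at q < s.
- A reader might infer that the protocol takes no account of death. It extracts death data; what is missing is an endpoint that uses them.
- A reader might take the cited composite of death or bronchopulmonary dysplasia as evidence on dose. It comes from a comparison of administration techniques. Only the separate remark on 200 mg/kg concerns dose and mortality, and it is worded as a possibility.
- A reader might infer that the 2-year gap also makes a life-saving dose look worse. That does not follow. It is a question of target population and follow-up.

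**Conclusion.** The point holds in limited form. The day-28, 36-week and duration endpoints have no death component and no mortality endpoint is listed, although the protocol raises a possible mortality effect of dose and extracts the data. Under the literal reading, the dose with fewer deaths looks worse whenever any additional survivor is on support: by 1.2 points in the main illustration and by 0.8 to 5.0 points over the wider assumed range. Among survivors it looks worse only if the additional survivors need support more often than the others. These sizes rest on assumed mortality and support rates and on no dose effect on support in the remaining infants. The primary endpoint is not part of this point. The conflict over 2-year follow-up is a separate inconsistency, for which no size can be given.

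**What to change.** - Define the day-28 and 36-week endpoints, in infants born at 32 weeks or less as in the secondary objectives, as death or respiratory support, and report each component.
- List death before neonatal discharge as a secondary endpoint.
- Analyse duration of support with death as a competing event, or replace it with support-free days over a stated window, with death scored zero.
- State that oxygen at discharge home is measured in infants discharged alive, and show it beside mortality.
- Reconcile sections 3, 5 and 9b on 2-year follow-up, and set the 2-year analysis population to the infants whose follow-up the study actually waits for. Say whether death before 2 years can be obtained, since the extracted field may not cover it.

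The cost is mainly wording, because the death fields for the neonatal stay are already in the extract and the sample size rests on the primary endpoint alone. The downside is that a composite mixes components and can mask opposing effects, which is why both must always be shown. Death between discharge and 2 years may need another data source.
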